7.5.1 Pharmacokinetic Assessment

The concentration in serum of loncastuximab tesirine PBD-conjugated antibody, total antibody and SG3199 unconjugated warhead will be assessed by a central laboratory designated by the Sponsor using validated bioanalytical methods.

Approximately 6 mL of whole blood will be collected as per SoE ([Table 2](#)). The predose PK samples will be collected preferably within 2 hours prior to start of infusion and at the end

(within -5 to +10 min) of Lonca infusion. Blood should be drawn from a vein away from the one used for study drug infusion.

Pharmacokinetic samples must be stored at -70°C. Please refer to the laboratory manual for detailed instructions regarding specimen handling and shipment.

7.5.2 Immunogenicity

Detection of ADAs will be performed by using a screening assay for identification of antibody positive samples/patients, a confirmation assay, and titer assessment, and will be performed using the Meso-Scale Discovery Electrochemiluminescence platform. If an ADA is confirmed, as appropriate, a functional assay for the assessment of the neutralizing capacity of the ADA will be performed.

Approximately 6 mL of whole blood will be collected as per SoE (Table 2). Blood should be drawn from a vein away from the one used for study drug infusion.

[figure not shown]
For patients who test positive for ADAs, an additional ADA sample may be requested for testing every 12 weeks following the EOT visit until the ADA titer falls to a background level.

ADA samples must be stored at -70°C. Please refer to the laboratory manual for detailed instructions regarding specimen handling and shipment.

7.5.3 CCI

[figure not shown]
7.5.3.1 CCI

CCI

7.5.3.2 CCI

CCI

7.6 Patient Reported Outcomes

Patient reported outcomes will be administered as per SoE ([Table 2](#)).

The impact of loncastuximab tesirine treatment on disease- and treatment-related symptoms, as well as various aspects of patient's health-related quality of life will be assessed by the following instrument:

- Functional Assessment of Cancer Therapy - Lymphoma (FACT-Lym)

Responses from patients will be captured via paper questionnaires.

All questionnaires will be completed in the respondent's native language, at the scheduled study visit prior to the patient seeing the investigator for any clinical assessment or treatment. Patients will provide responses at the study site. The patient will be given enough instructions, space, time and privacy to complete the questionnaires by themselves and without any assistance from anyone else. The study coordinator encourages the patient to complete the questionnaire without any missing responses.

While completing the questionnaire, some respondents might ask questions indicating they are having difficulty reading the PRO questionnaires. For example, a respondent may ask the meaning of specific items or response options so that he/she can better understand and respond. If this occurs, an interviewer may assist the respondent by re-reading the question or response options for him/her verbatim. If the respondent asks the interviewer to interpret the meaning of an item or response options, no explanation or interpretation will be offered but suggest that the subject use his/her own interpretation of the question and response options. Respondents answer the questions based on what they think the questions mean.

If a respondent is having difficulty with the response choices (for example, he or she may say "I don't know" or something different than what is stated on the questionnaire), it is important to direct the respondent to pick the response that best fit how he/she feels. The respondent must not record a response that is not one of the provided response options for each question (e.g., respondent does not write in his/her own response). The interviewer may re-read the response choices verbatim; however, do not rephrase the response choices or try to simplify the language.

FACT-Lym

FACT-Lym (see [Appendix 12.3](#)) is a lymphoma-specific subscale for the Functional Assessment of Cancer Therapy (FACT) questionnaire ([Hlubocky et al., 2013](#)). It consists of 15 specific items that are used together with the core 27-item questionnaire FACT-G. The patient is asked to respond to each item with a score of 0–4, where 0 = not at all, 1 = a little bit, 2 = somewhat, 3 = quite a bit, and 4 = very much. A higher score indicates a worse level of QoL.

8 Adverse Events Reporting

Reporting of AEs to competent authorities and Independent Review Boards (IRBs)/Independent Ethics Committees (IECs) will be consistent with current laws, regulations, and guidelines.

8.1 Definition of Adverse Events and Serious Adverse Events

8.1.1 Adverse Events

An AE is defined as any untoward medical occurrence in a patient or clinical investigation subject administered a pharmaceutical product, which does not necessarily have to have a causal relationship with this treatment.

An AE does not include the following:

- Medical or surgical procedures such as surgery, endoscopy, tooth extraction, and transfusion. The condition that led to the procedure may be an AE and must be reported.
- Pre-existing diseases, conditions, or laboratory abnormalities present or detected before the screening visit that do not worsen.
- Situations where an untoward medical occurrence has not occurred (e.g., hospitalization for elective surgery, social and/or convenience admissions)

Test results collected during the study (e.g., laboratory values, physical examination, ECGs, etc.) or identified from review of other documents may constitute AEs if deemed clinically significant.

8.1.2 Serious Adverse Events

An SAE is defined as any AE that:

- results in death.
- is life threatening (Note: The term “life-threatening” in the definition of “serious” refers to an event in which the subject was at risk of death at the time of the event; it does not refer to an event that hypothetically might have caused death if it were more severe.).
- requires inpatient hospitalization or prolongation of existing hospitalization (hospitalization for elective procedures or for protocol compliance is not considered an SAE).
- results in persistent or significant disability/incapacity.
- is a congenital anomaly/birth defect.
- important medical events that do not meet the preceding criteria but based on appropriate medical judgment may jeopardize the patient and may require medical or surgical intervention to prevent any of the outcomes listed above. Examples of medically important events include intensive treatment in an emergency room or at home for allergic bronchospasm; blood dyscrasias or convulsions that do not result in hospitalization; and development of drug dependency or drug abuse. For the avoidance of doubt, infections resulting from contaminated pharmaceutical product will be considered a medically important event and subject to expedited reporting requirements.

8.1.3 Clinical Laboratory Abnormalities and Other Abnormal Assessments as Adverse Events or Serious Adverse Events

Laboratory abnormalities (e.g., clinical chemistry, hematology, and urinalysis) or other abnormal assessments (e.g., electrocardiogram, x-rays, vital signs) without clinical significance are not recorded as AEs or SAEs. However, laboratory abnormalities/other abnormal assessments that require medical or surgical intervention or lead to pharmaceutical product interruption, modification, or discontinuation must be recorded as an AE, as well as an SAE, if applicable. If the laboratory abnormality/other abnormal assessment is consistent with a clinical diagnosis, report the AE using the diagnosis (i.e., anemia), not the laboratory result (i.e., decreased hemoglobin).

8.2 Eliciting and Reporting Adverse Events/Serious Adverse Events

Patients will be instructed to contact the Investigator at any time after ICF signature if any symptoms develop. At each study visit, patients will be asked a nonleading question to elicit any medically related changes in their well-being. Patients may also report AEs voluntarily and they will be instructed to contact the Investigator between visits if any symptoms develop or worsen.

AEs will be reported starting when the patient provides written informed consent. Clinically significant medical conditions present at the time of ICF signature will be reported as medical history. Clinically significant medical conditions that start or worsen after ICF signature will be reported as AEs.

All AE/SAEs regardless of relationship to study drug, will be reported from the time the patient signs the ICF until 15 weeks after the last dose of study drug or the start of new anti-cancer therapy, whichever is earlier; thereafter only related SAEs will be reported.

Whenever possible, AEs should be reported as a diagnosis rather than individual signs and symptoms. If no diagnosis is available or has been identified, then the primary symptom is reported.

In general, the term ‘disease progression’ should not be used for reporting an AE/SAE. However, AEs/SAEs that are complications of disease progression should be reported.

All AEs reported or observed during the study will be recorded on the AE page of the eCRF. Information to be collected will include event term, date of onset, assessment of severity ([Section 8.3](#)), seriousness ([Section 8.1](#)), relationship to study drug ([Section 8.4](#)), action taken with study drug, date of resolution of the event or ongoing (when no resolution by the end of the reporting period), any required treatment or evaluations, and outcome.

New SAEs and any recurrent episodes, progression, or complications of the original SAE must be reported to the drug safety department of the Sponsor or delegate (e.g., contract research organization [CRO]) within 24 hours after the time site personnel first learn about the event. Reporting will occur through the EDC system.

8.3 Assessment of Severity

The AEs will be graded according to Common Terminology Criteria for Adverse Events (CTCAE) v5.0. For events not included in the CTCAE criteria, the severity of the AE is graded on a scale of 1 to 5 as shown in [Table 6](#).

Table 6 **Definition of Severity Grades for CTCAE**

Grade	Definition
1	Mild; asymptomatic or mild symptoms; clinical or diagnostic observations only; intervention not indicated.
2	Moderate; minimal, local or noninvasive intervention indicated; limiting age appropriate instrumental activities of daily living (ADL). ^a
3	Severe or medically significant but not immediately life threatening; hospitalization or prolongation of hospitalization indicated; disabling; limiting self-care ADL. ^b
4	Life-threatening consequences; urgent intervention indicated.
5	Death related to adverse event.

^a ADL refers to preparing meals, shopping for groceries or clothes, using the telephone, managing money, etc.

^b Self-care ADL refers to bathing, dressing and undressing, feeding self, using the toilet, taking medications, and not bedridden.

The AEs characterized as intermittent do not require documentation of onset and duration of each episode.

8.4 Assessment of Causality

The Investigator's assessment of an AE's relationship to study drug is an important part of safety reporting, but is not a factor in determining whether an AE is reported. An AE will be assessed as related to study drug if there is a reasonable possibility of causal relationship with the use of the study drug. For SAEs, whenever possible, the Investigator should provide a rationale for the causality assessment.

The investigator or qualified subinvestigator is responsible for providing an assessment of the relationship to the study drug(s) using clinical judgment and the following considerations:

Causality	Definition
Not related	An adverse event is not related to the study drug
Unlikely related	An adverse event where evidence exists for an alternative explanation other than the study drug e.g., concomitant medication(s), concomitant disease(s), or time to onset suggests unlikely relationship.
Possibly related	An adverse event that might be due to study drug. An alternative explanation (e.g., concomitant medication(s), concomitant disease(s), or time to onset) is inconclusive, where a causal relationship with study drug cannot be ruled out.
Probably related	An adverse event that might be due to study drug. An alternative explanation (e.g., concomitant medication(s), concomitant disease(s)) is less likely, and where a causal relationship with study drug is more suggestive (i.e., time to onset, positive dechallenge/rechallenge).
Related	An adverse event where an alternative explanation cannot be explained and, therefore, considered related to study drug.

8.5 Special Situations Reports

8.5.1 Definitions of Special Situations

Any special situation occurring in a participant that may require expedited reporting or safety review may include the following with the study drug:

- Pregnancy reports (see [Section 8.5.2](#))
- Overdose reports (see [Section 8.5.3](#))
- Other special situations (see [Section 8.5.4](#)), such as:
 - Suspected misuse or abuse
 - Accidental exposure
 - Medication error
 - Exposure to the study drug from breast-feeding
 - Adverse events associated with product complaints
 - Suspected transmission of an infectious agent via a medicinal product, which will be classified as an SAE

8.5.2 Reporting Pregnancy

Any pregnancy in a patient that occurs from signing the ICF up to 12 months after last dose of study treatment must be reported using the Pregnancy Report Form. Any pregnancy in a partner of a male participant that occurs from signing the ICF up to 7 months after last dose of study treatment must be reported.

Pregnancy must be reported within 24 hours after the site personnel first learn of the pregnancy. The pregnancy itself is not considered an AE. However, the pregnancy must be followed to determine outcome (including spontaneous miscarriage, elective termination, normal birth, or congenital abnormality) and status of mother and child, even if the patient discontinued from the study. Abortions (elective or spontaneous) occurring during the pregnancy reporting period must be reported as an SAE.

Any SAE occurring in association with a pregnancy that is brought to the Investigator's attention after the patient has completed the study and considered by the Investigator as possibly related to the study drug must be promptly reported in the same manner.

Once pregnancy is confirmed in a study participant, study drug will be discontinued, see [Section 7.4.6](#) for additional information.

8.5.3 Reporting Overdose

An overdose of the study drug(s) is defined under [Section 6.6](#).

An overdose itself is not considered an AE. However, if such an overdose occurs during the study, with or without any signs or symptoms, it must be reported to drug safety department of the Sponsor or delegate (e.g., CRO) within 24 hours after the time site personnel first learn about the event.

8.5.4 Reporting Other Special Situations

All other special situation reports must be reported to drug safety department of the Sponsor or delegate (e.g., CRO) within 24 hours after the time site personnel first become aware of the situation.

8.6 Data Monitoring Committee

A data monitoring committee (DMC) will primarily review the collection of AEs and other safety-related information on a periodic basis to ensure the safety of patients enrolled in this study. They will provide expertise and make recommendations, based on independent evaluation, on study conduct and progress, which concern the continuation, modification, or termination of the study. The DMC will be composed of at least one clinician with lymphoma expertise and a biostatistician.

Details regarding the DMC responsibilities, authorities, and procedures will be included in a separate and mutually agreed DMC charter.

9 Statistical Considerations

Full details of the analysis plan, including a more technical and detailed elaboration of the statistical analyses will be provided in the statistical analysis plan (SAP). The SAP will be developed and finalized before database lock.

9.1 Sample Size Determination

A sample size of 40 patients for each cohort is considered adequate to assess safety and efficacy in the corresponding study population. [Table 7](#) lists estimated CR rate and the corresponding 95% exact CIs by number of responders from a sample size of 40 patients.

Table 7 Estimated Complete Response Rate and 95% CI for each cohort

Number of Patients	Number of Responders	CRR	95% CI for CRR (Exact)
40	12	30%	(16.6, 46.5)
40	16	40%	(24.9, 56.7)
40	20	50%	(33.8, 66.2)
40	24	60%	(43.3, 75.1)

Abbreviations: CI, confidence interval; CRR, complete response rate; ORR, overall response rate.

9.2 Analysis Populations

- All-Treated Population: All patients who receive at least 1 dose of study drug. This population will be used in the primary analyses of efficacy and safety for both cohorts.
- Patient-reported Outcomes Population: All patients who receive at least one dose of study treatment and complete at least one questionnaire at baseline and at one post baseline visit.
- The PK Population: All patients who receive study drug and have at least 1 pre- and 1 post-dose valid PK assessment.
- The Immunogenicity Population: All patients who receive study drug and have at least 1 valid anti-drug antibody assessment.
- **CCI**

9.3 Interim Analysis

No formal interim analysis is planned.

9.4 Final Analysis

All efficacy and safety endpoints will be analyzed and reported in the clinical study report (CSR).

9.5 Demographics and Baseline Characteristics

Demographics and Baseline characteristics, such as cancer history and medications history, will be summarized for the All-treated Population (Cohort A and Cohort B).

9.6 Exposure to Treatments

Exposure to study drug, prior, and concomitant medications will be summarized for the All-Treated Population by dose level. Dose interruptions, reductions, and relative dose intensity will also be summarized.

9.7 Efficacy Analyses

Primary efficacy analyses will be based on response as determined by treating investigator.

9.7.1 Complete Response Rate

The CR rate will be defined as the proportion of patients with a best overall response (BOR) of CR, based on response assessments obtained on or prior to the start of subsequent cancer treatment. The percentage of CR rate with its 95% CI will be presented. For the primary CR rate analysis, patients with missing response or not evaluable information will be counted as failures. Further details will be provided in the SAP.

9.7.2 Overall Response Rate

The ORR will be defined as the proportion of patients with a BOR of CR or PR. The overall response category will be derived based on response assessment performed on or before the start of subsequent anti-cancer therapy. For the primary ORR, patients with a CR or PR will be counted as successes and all other patients (including those with missing response information) will be counted as failures.

The ORR with its 95% CI will be presented. In contrast to CR, PR, or PD, a BOR of SD can only be made after the patient is on-study for a minimum of 35 days after the first dose of study drug (Cohort A and Cohort B). Any tumor assessment indicating SD before this time period will be considered as a non-evaluable for BOR if no assessment after this time period is available.

9.8 Safety Analyses

Safety analyses will be presented descriptively.

9.8.1 Adverse Events

The focus of AE summarization will be on TEAEs. A TEAE is defined as an AE that occurs or worsens in the period extending from the first dose of study drug to 15 weeks after the last dose of study drug in this study or the start of a new anticancer therapy, whichever is earlier.

All TEAEs will be summarized. Summary tables will be presented to show the number of patients reporting TEAEs by severity grade and corresponding percentages. A patient who reports multiple TEAEs within the same Preferred Term (or System Organ Class) is counted only once for that Preferred Term (or System Organ Class) using the worst severity grade.

Separate summaries will be prepared for TEAEs classified as severe or life-threatening (\geq Grade 3); study drug-related AEs; AEs leading to treatment interruption, modification, or discontinuation; AEs of special interest; SAEs; and death.

9.8.2 Clinical Laboratory Results

Clinical hematology, biochemistry, and urinalysis data will be summarized at each scheduled assessment. Shifts for clinical laboratory results that can be graded according to CTCAE v5.0 (or more recent) will be summarized by CTCAE grade. Shifts for other numeric laboratory results will be by high/normal/low flag. Shifts for all other laboratory results will be by normal/abnormal flag.

Summaries by visit will include data from scheduled assessments, and all data will be reported according to the nominal visit date for which it was recorded. Unscheduled data will be included in “worst-case post-Baseline” summaries, which will capture a worst case across all scheduled and unscheduled visits after the first dose of study drug. Further details will be provided in the SAP.

9.8.3 Additional Safety Assessments

The results of scheduled assessments of vital signs, physical examinations, ECOG performance status, and 12-lead ECGs will be summarized. All data will be reported according to the nominal visit date for which it was recorded (i.e., no visit windows will be applied). Unscheduled data will be included in “worst case” summaries, which will capture a worst case across all scheduled and unscheduled visits after the first dose of study drug. All data will be listed. Further details will be provided in the SAP.

9.9 Pharmacokinetic Analysis

For the PK-evaluable patients, PK parameters will be determined for the typical patient and estimated for individual patients using a population PK analysis method. Analysis will consider model development for conjugated antibodies (Ab) and total Ab. If supported by available data, the model may also include characterization of SG3199 unconjugated measures. Intrinsic and extrinsic factors which may have influence on PK parameter variability will be tested and assessed for inclusion in the final model. Demographic data for the PK population will be summarized. Potential correlations of PK parameters to safety and efficacy endpoints, as appropriate, may be evaluated. Results of the population PK analysis will be reported separately.

9.10 Immunogenicity Analysis

Anti-drug antibody will be measured for Lonca-R arm during the study using screening and confirmatory assays with titer evaluation ([Figure 3](#)).

[figure not shown]

Figure 3 Anti-drug Antibody Tiered Immunogenicity Testing Strategy

Abbreviations: ADA, anti-drug antibody; ADCT-402, loncastuximab tesirine; BSA-SG3249, bovine serum albumin conjugated to SG3249; Intermediate monoclonal antibody RB4v1.2; irrelevant monoclonal antibody B12 based ADC B12-SG3249; NF, normalization factor; PK, pharmacokinetics; SCP, screening cut-point.

Results from ADA testing will include tabular summarization for number/proportion of patients with confirmed positive predose ADA response, confirmed number of patients with postdose ADA response only, confirmed number of patients with positive ADA response at any time, and confirmed positive ADA before and after dose. The denominator will be the total number of patients tested for ADAs in the study.

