8. Pregnancy test will be limited to females of childbearing potential; a final pregnancy test should be performed ≥ 12 months after the last dose of study drug has been administered (remote testing may be performed).
9. For days of loncastuximab tesirine infusion, PK will be collected predose (preferably within 2 h prior to start of infusion), and at the end (within -5 to +10 min) of Lonca infusion.
10. ADA samples will be collected predose (preferably within 2 h prior to start of infusion) on C1D2, C2D1 and then every other cycle beginning with C4. Patients who test positive for ADAs may be requested to supply additional ADA samples.

CCI

12. PRO instrument should be completed prior to clinical assessment.
13. Patients in both cohorts will receive 1 additional cycle of assigned therapy (Cycle 4) if in CR and 3 additional cycles if PR (Cycles 4-6) based on PET-CT after Cycle 3. Patients in cohort B who achieve stable disease and are receiving clinical benefit may receive 3 additional cycles (Cycles 4-6).
14. Premedication for the Lonca-R regimen consists of dexamethasone 4 mg PO/IV BID $\times 3$ days beginning the day prior to loncastuximab tesirine; premedication(s) for rituximab will be given according to institution standard.

Visit Scheduling Windows:

- Treatment Period: C1D1 is the reference day, otherwise visit day ± 2 days, except of visit day 2 where the time window is +2 days.
- EoT: Patients who complete all assigned treatment cycles of treatment should have their EoT visit performed 28 (± 7) days from the last dose of study treatment, and in any case prior to the initiation of new anticancer treatment.
- Follow-up Period: visit day ± 14 days.

1 Introduction and Background

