Cohort A and Cohort B: 
• Further evaluate the efficacy of Lonca-R• To characterize the safety profile of Lonca-R• To characterize the PK profile of Lonca when given in combination with rituximab• To evaluate the immunogenicity of Lonca when given in combination with rituximab• To evaluate the impact of Lonca-R treatment on treatment-related and disease-related symptoms, patient-reported functions, and overall health status	Cohort A and Cohort B: 
• ORR according to the 2014 Lugano Classification, defined as the proportion of patients with a BOR of CR or PR.• 2-year PFS, defined as the proportion of patients that are PFS event-free at 2 years.• 3-yr OS, defined as the proportion of patients that are OS event-free at 3 years.• DoR defined as the time from the first documentation of tumor response (CR or PR) to disease progression or death• Frequency and severity of AEs and SAEs.

Objectives	Endpoints
	
• Changes from baseline in safety laboratory variables, vital signs, physical examinations, ECOG PS• Concentrations and PK parameters of loncastuximab tesirine PBD-conjugated antibody, total antibody, and SG3199 unconjugated warhead• Frequency of confirmed positive ADA responses, their associated titers and, if applicable, neutralizing activity to loncastuximab tesirine after treatment with loncastuximab tesirine when given in combination with rituximab• Changes in patient-reported outcomes (e.g., symptoms, functions, and overall health status) from baseline as evaluated by FACT-Lym
Exploratory	
CCI	CCI

Abbreviations: ADA, anti-drug antibody; AE, adverse event; BOR, best overall response; CR, complete response; DLBCL, diffuse large B-cell lymphoma; DoR, duration of response; EoT, end of treatment; ECOG PS, Eastern Cooperative Oncology Group scale of performance status; FACT-Lym, Functional Assessment of Cancer Therapy-Lymphoma; Lonca-R, loncastuximab tesirine and rituximab; ORR, overall response rate; OS, overall survival; PBD, pyrrolobenzodiazepine; PFS, progression free survival; PK, pharmacokinetic; PR, partial response; PS, performance status; R-CHOP, combination of rituximab, cyclophosphamide, doxorubicin, vincristine, and prednisone, SAE, serious adverse event.

4 Study Design

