4.1 Overview

This is a Phase 2 open-label, study of Lonca-R in previously untreated unfit/frail patients with DLBCL. The study will include a Screening Period (up to 28 days), a Treatment Period (4-6 cycles [each of 3 weeks]), and a Follow-up Period (for up to 5 years after treatment discontinuation) ([Section 4.2](#)).

A response-adapted approach will be used in this study. Two parallel cohorts will enroll patients in the study. Cohort A will enroll unfit patients and Cohort B will enroll frail patients or patients with cardiac comorbidities. Cohort A will assess efficacy and Cohort B will assess the efficacy and tolerability of Lonca-R. Fitness and frailty of the patients will be assessed based on the sGA tool developed by the FIL ([Merli, 2021](#)). See [Section 7.2](#) for details about sGA.

The study will enroll approximately 80 patients (approximately 40 patients in each cohort).

Based on the results from Cohort A and/ or B a protocol amendment will be considered to further evaluate the Lonca-R combination in these patient populations.

Enrolled patients in both cohorts will receive Lonca-R for 3 cycles. Patients who achieve CR after 3 cycles of Lonca-R treatment will continue to receive one additional cycle of Lonca-R. Patients who achieve PR after 3 cycles of Lonca-R will continue to receive additional 3 cycles of Lonca-R. Additionally, for Cohort B only, patients who achieve SD and derive clinical benefit per the treating physician may also continue to receive additional 3 cycles of Lonca-R. Details of dosing regimen are described in [Section 6.3 \(Table 4\)](#), (see [Figure 2](#)).

The duration of the study participation for each patient is defined as the time from the date of signed written informed consent to the completion of the follow-up period, withdrawal of consent, loss to follow-up, or death, whichever occurs first. Each patient enrolled in both cohorts will have the same duration of study participation.

18 weeks) or unacceptable toxicity, or other discontinuation criteria (see [Section 5.5](#)), whichever occurs first. Details of the treatment regimen are described in [Table 4](#).

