4.1.4 Immunogenicity Population

All patients who receive study drug and have at least 1 valid anti-drug antibody assessment.

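### Post-dose ADA rates are divided by every patient tested, so a patient with only a pre-dose sample counts as negative; the effect may be nil and is probably small

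*Protocol*

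**What the plan says.** - **Denominator.** Protocol Section 9.10 plans four summaries: positive before dosing, positive after dosing only, positive at any time, and positive both before and after. In its words, the middle two are "confirmed number of patients with postdose ADA response only, confirmed number of patients with positive ADA response at any time". One rule covers all four: "The denominator will be the total number of patients tested for ADAs in the study".
- **Population.** SAP Section 4.1.4, like Protocol Section 9.2, defines the Immunogenicity Population as "All patients who receive study drug and have at least 1 valid anti-drug antibody assessment". It does not say when the sample must have been taken.
- **Sampling.** Footnote 10 of the Schedule of Events (Protocol Table 2) places pre-dose ADA samples "on C1D2, C2D1 and then every other cycle beginning with C4". The table also marks an ADA sample at the end-of-treatment (EoT) visit.
- **Endpoint.** Protocol Section 3, Table 3, has as a secondary endpoint the frequency of confirmed ADA, its titers and, if applicable, "neutralizing activity to loncastuximab tesirine after treatment with loncastuximab tesirine when given in combination with rituximab".
- **Contrast.** In the same Section 9.2, the PK Population must "have at least 1 pre- and 1 post-dose valid PK assessment". The patient-reported outcomes population likewise needs a baseline and a later questionnaire.
- **SAP.** Section 2.2 keeps the immunogenicity objective and Section 3.4 lists no change to the protocol's statistics. There is no ADA analysis section.

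**The concern.** The C1D2 sample is drawn before any loncastuximab tesirine is given. A patient who contributes that sample and no other belongs to the Immunogenicity Population and to the Section 9.10 denominator, but cannot enter the numerator of the post-dose-only or before-and-after category. Dividing by all tested patients treats absence of a post-dose result as a negative post-dose result.

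The endpoint is about ADA after treatment, and such a patient carries no information on it. The rule can move these two rates in one direction only, downward relative to the rate among patients who could be assessed. It is a stated rule and not a gap in detail, and nothing elsewhere in the protocol or SAP corrects it.

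What is at stake is the accuracy of a descriptive secondary endpoint. No primary endpoint, test or sample-size argument depends on it.

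**Working it through.** **No figure to reproduce.** Neither document states an ADA rate. The exact (Clopper-Pearson) interval code used below was checked against Protocol Table 7 and returns its four 95% intervals: 12/40 gives 16.6 to 46.5, 16/40 gives 24.9 to 56.7, 20/40 gives 33.8 to 66.2, and 24/40 gives 43.3 to 75.1.

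**Inputs**
- N, number tested: 41, assuming every patient treated by 20 July 2023 (SAP Section 3.2) was tested.
- x, number post-dose positive: 4, assumed.
- m, number with no post-dose sample: not in the documents; varied from 0 to 8.
- No patient lacks a valid baseline sample: assumed, so that m alone separates tested from evaluable.

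**Formulas**
- Rate as planned: x / N
- Rate among evaluable patients: x / (N − m)
- Relative understatement: 1 − (x/N) ÷ (x/(N − m)) = 1 − (N − m)/N = m/N, whatever x is (provided x is at least 1)

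**Results for N = 41, x = 4.** The planned rate is 4/41 = 9.8% (95% CI 2.7 to 23.1) in every row.

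| m | Evaluable rate | 95% CI | Understatement m/N |
|---|---|---|---|
| 0 | 4/41 = 9.8% | 2.7 to 23.1 | 0% |
| 1 | 4/40 = 10.0% | 2.8 to 23.7 | 2.4% |
| 2 | 4/39 = 10.3% | 2.9 to 24.2 | 4.9% |
| 4 | 4/37 = 10.8% | 3.0 to 25.4 | 9.8% |
| 8 | 4/33 = 12.1% | 3.4 to 28.2 | 19.5% |

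For one cohort at its planned size ("approximately 40 patients in each cohort"), with x = 4 and m = 4, the rate is 4/40 = 10.0% as written and 4/36 = 11.1% among evaluable patients, with m/N = 10.0%.

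**How large m can plausibly be.** Protocol Section 5.5.1 asks patients who stop treatment to attend an EoT visit, and Section 4.2.3 sets that visit 28 (±7) days after the last dose. A patient who stops after Cycle 1 for toxicity or progression therefore still has a scheduled post-dose ADA sample. Those left with only the C1D2 sample are mainly patients who die, withdraw consent (Section 5.5.2 ends data collection at that point) or are lost before both C2D1 and EoT, plus any whose later samples are missed or invalid.

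**The other two categories.** Patients with only a pre-dose sample belong in the pre-dose denominator, so they do not distort that rate. The any-time category mixes pre-existing and post-dose antibody, so such a patient can be positive there.

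**The case against.** The strongest reply is that the EoT sample nearly closes the gap. With 1 or 2 patients affected, the illustrative rate moves from 9.8% to 10.0% or 10.3%, far inside an interval of 2.7 to 23.1%. The denominator is openly stated, the endpoint is descriptive, and the study has been discontinued. All of this stands and limits the size of the point. It does not make a patient without a post-dose sample a post-dose negative.

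A reader might go further in four ways that the documents do not support:

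- **That post-dose ADA is understated by some definite amount, such as 10 to 20%.** No count of patients without a post-dose sample is given, and the range must start at zero.
- **That the evaluable-patient rate is the true rate.** That holds only if patients without a post-dose sample would have developed ADA as often as the others. They have had less exposure and follow-up, so this cannot be assumed.
- **That the bias is worse in the frail cohort.** Neither document gives early-discontinuation rates by cohort, and Section 9.10 does not say that ADA results are split by cohort. The one cohort-specific stopping rule, in Section 5.5.1, is stricter for Cohort A and applies after Cycle 3, when C2D1 has already passed.
- **That the SAP made the error its own.** SAP Section 4.1.4 defines a population and sets no denominator. SAP Section 1 says that, after the discontinuation, it does not cover every protocol analysis.

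It is also fair to object that requiring a baseline sample for every post-dose rate would drop a post-dose positive patient who has none. The fix allows for this.

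**Conclusion.** The point holds, as a minor one. Under Section 9.10, a patient with only the C1D2 sample is counted as negative in the post-dose-only and before-and-after rates. These rates fall below the rate among evaluable patients by the fraction m/N. If m = 0 there is no effect.

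The direction follows from the text; the size does not. The 9.8% against 10.0 to 12.1% for m from 1 to 8 rests on assumed values of N, x and m, and the schedule makes the lower end more likely. The primary endpoints and the sample size are untouched.

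**What to change.** In Protocol Section 9.10, and in any SAP that reports ADA, replace the single denominator with one for each rate:

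- **Pre-dose prevalence:** patients with a valid baseline sample.
- **Post-dose only, and before and after:** patients with a valid baseline sample and at least 1 valid post-dose sample.
- **Any overall post-dose positive rate:** patients with at least 1 valid post-dose sample. This keeps a post-dose positive patient who has no baseline result.
- **Any time:** all tested patients, labelled as including pre-existing ADA.

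Report the number evaluable and not evaluable beside each rate.

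The cost is a few lines of text. No visit or sample is added, and the change can be applied to data already collected. The denominators become slightly smaller and a reported rate may be slightly higher. If every tested patient has a valid baseline and a valid post-dose sample, no figure changes.
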